10 TREATMENT OF STUDY PARTICIPANTS

10.1 The Product(s)

Where possible, the 4-dose vial formulations of two licensed products, Synflorix and Prevnar13, will be used in this study (Table 3).

If the 4-dose vial formulation is not available in time for the study to start due to reasons out of the investigators' control e.g. in the manufacture and/or supply of the 4-dose vials, single dose formulations will be used as specified below.

Table 3. Specifications of the two vaccines included in the study.

Manufacturer	Commercial name	Target serotypes	Conjugate protein(s)	Adjuvant	Presentation
GlaxoSmithKline plc.	Synflorix; PCV10	1, 4, 5, 7F, 9V, 14, 18C, 19F, 23F, 6B	Protein D (outer membrane protein from Non-Typeable Hib), or Diphtheria Toxoid (serotype 19F only), or Tetanus Toxoid (serotype 18C only)	Aluminum phosphate	Suspension for intramuscular injection; 1, 2 or 4 dose vials
Pfizer Inc.	Prenar13; PCV13	1, 4, 5, 7F, 9V, 14, 18C, 19F, 23F, 6B, 3, 6A, 19A	Diphtheria CRM ₁₉₇	Aluminum phosphate	Suspension for intramuscular injection; 1 dose pre-filled syringe or 4 dose vials

10.2 Dose selection

Fractional doses will be administered according to specific vaccine preparation and administration SOPs. The antigen doses included in each full and fractional dose administration are documented in Table 4.

Table 4. The antigen dose in the available full dose vaccine formulations and the estimated antigen dose in the proposed fractional (20% and 40%) dose formulations.

Vaccine formulation	Vaccine-serotype specific saccharide dose per administration (µg)												
	1	3	4	5	6A	7F	9V	14	18C	19A	19F	23F	6B
PCV13	2.2	2.2	2.2	2.2	2.2	2.2	2.2	2.2	2.2	2.2	2.2	2.2	4.4
40%-PCV13	0.88	0.88	0.88	0.88	0.88	0.88	0.88	0.88	0.88	0.88	0.88	0.88	1.76
20%-PCV13	0.44	0.44	0.44	0.44	0.44	0.44	0.44	0.44	0.44	0.44	0.44	0.44	0.88
PCV10	1.0		3.0	1.0		1.0	1.0	1.0	3.0		3.0	1.0	1.0
40%-PCV10	0.40		1.2	0.40		0.40	0.40	0.40	1.20		1.20	0.40	0.40
20%-PCV10	0.2		0.6	0.2		0.2	0.2	0.2	0.6		0.6	0.2	0.2

10.3 Product management & storage

Vaccine stocks will be obtained from appointed distributors of the manufacturers. For each batch documentary evidence will be obtained to ascertain origin of products, and to demonstrate maintenance of cold chain from manufacturer to the distributor. The vaccine will be held at a central store, refrigerated at +2 °C to +8 °C, and dispensed to clinic sites as necessary. Vaccine will be continually temperature monitored and the number of excursions and cumulative time outside of the refrigerator will be recorded.

Vials will be discarded if total time between 8°C and 25°C exceeds 4 days (96 hours) as indicated by the vaccine vial monitor (VVM)[60, 61].

Vials will be discarded if the vaccine ever freezes.

The 4-dose vials will be used until the 28th day following the first puncture as per WHO recommendations[73], provided that:

- The expiry date has not passed.
- The vaccines are stored under appropriate cold chain conditions.
- The vaccine vial septum has not been submerged in water.
- Aseptic technique has been used to withdraw all doses.
- The vaccine vial monitor (VVM), if attached, has not reached the discard point (see package insert or study specific vaccine preparation and administration SOPs).

The date of first puncture and number of administrations from each vial will be recorded by vaccinating nurses according to vaccine preparation and administration SOPs.

If single dose formulations are used, which do not contain preservative, a single full/fractional dose will be administered as per vaccine preparation and administration SOPs and the remaining volume will be discarded on the day of first puncture as per WHO recommendations[73].

10.4 Dispensing Procedures

The study vaccinating nurse will be responsible for preparation and administration of the vaccines as randomised. They will be responsible for the accompanying documentation.

The vaccine dose to be administered will be guided by the randomization process. The dose will be a full dose (0.5ml), a 40% dose (0.2ml) or a 20% dose (0.1ml) administered intramuscularly in the anterolateral thigh.

Any concomitant routine immunisations will be administered according to the routine immunisation schedule instructions. Site of all vaccinations will be recorded in clinical source documents.

10.5 Unblinding

The primary endpoint of immunogenicity will be assessed at 4 weeks post-third dose administration. The trial data and safety monitoring board (DSMB) will review the results and if the non-inferiority criteria are not met as per the statistical analysis plan, the DSMB will authorise unblinding in order to allow a full dose of vaccine to be administered to fractional dose recipients.

Prior to this time point, unblinding will not be necessary unless as per DSMB request for SAE review; apart from those participants in trial arm G. Study staff and parents of participants enrolled in trial arm G will become unblinded to the allocation at the clinic visit at 10 weeks of age, due to the difference in the PCV schedule. Blinding beyond 10 weeks could be maintained through a placebo injection given to the other 6 arms, however, the discomfort to the participants would outweigh any benefit to the participant or the study. As long as blinding is maintained among trial arms A-F, the unblinding of arm G is unlikely to impact the main outcome assessments (objective assessments of immunogenicity and carriage) or retention (participants in trial arms A-F would remain with a 33% chance of being allocated to the full dose arms).

10.6 Prior/Concomitant Therapy

Concomitant therapy will be documented, the site of administration of concomitant vaccines will be documented. Previous PCV vaccination or planned PCV uptake under the routine immunisation programme, outside of the trial, will be noted for exclusion.

10.7 Rescue vaccination

The primary endpoint of immunogenicity will be assessed at 4 weeks post-third dose administration. The DSMB will review the immunogenicity results from the time point at 4 weeks post-third dose and if the non-inferiority criteria are not met as per the statistical analysis plan, the DSMB will authorize unblinding in order to allow a full dose of vaccine to be administered to fractional dose recipients as a rescue dose.

The study is not powered to allow non-inferiority to be assessed in a subset of the immunogenicity samples therefore results from all participants will be required prior to DSMB review. The timing of the shipments of samples to UCL, the immunological analyses and the DSMB review meeting will mean that the outcome of the DSMB's review may only be available when some of the trial participants have already exited trial follow-up. If participants undergo their last study visit before the DSMB has reviewed all the data, the contact information for the participant's parents will be updated by study staff at their last study visit and they will be told they will be contacted by study staff in the near future and may be asked to return to the clinic for an additional vaccination. Fieldworkers and/or community health volunteers (CHVs) will be employed to keep in touch with any participants who have already exited the trial before the DSMB review in order to invite them back to the clinic if necessary. All participants will be recruited in Kilifi County where the risk of morbidity attributable to pneumococcal vaccine types is very low (see Ethics section 18).

Any child who develops vaccine type invasive pneumococcal disease will be unblinded and withdrawn from the study. If the child was allocated to a reduced dose arm, they will be given full dose PCV10 in three doses 4 weeks apart (if aged <12 months) or 1 dose (if aged ≥12 months).

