Infants will receive the first dose of the three-dose schedule at 6 weeks of age and then mothers and infants will be invited back to the study clinic 6 further times during the course of the study. Infants will receive the 2nd and third doses of the vaccine, at 10 and 14 weeks or at 14 weeks and 9 months of age. They will have a small amount of blood taken at their first visit, and 4 weeks after the 2nd and 3rd doses, some participants will also have a small amount of blood drawn at the time of the 3rd dose and at their last study visit at 18 months of age. Two swabs will be taken from the mucous in the nose to look for the presence of the bacteria.

What are the benefits and risks/costs of the study for those involved? There is a small risk that the children in this study who receive the lower dose schedules will be less well protected than those who receive the full dose. However, because the vaccine has been in use for 6 years already in Kenya and will continue to be in use in the routine immunization system throughout the study, the bacteria is much less common than it was and the likelihood of developing disease is very low. As participants in the study, infants will have access to the study medical staff and will be able to present with any illness at an early stage and receive free treatment and/or referral to the sub-district hospital up until the age of 18 months (when the study ends). If, after final analyses, the lower doses are found to not give a good enough immune response, all infants in those groups will be given a single booster vaccination with the full dose.

If a low dose of the vaccine stimulates a protective immune response, infants who were randomly selected to be given the PCV13 will have the added benefit of immunization against three additional pneumococcal bacterial types (3, 6A, 19A) contained in the study vaccine (PCV13) but not contained in the vaccine used in the national programme (PCV10). 900 of the 2100 children recruited into the study will receive PCV13.

How will the study benefit society? If the pneumonia vaccines are effective at lower doses, the whole community may benefit. If lower doses can be administered the cost of the vaccine will fall meaning it may continue to be delivered by the government for longer.

When does the study start and finish? The study will start upon receipt of ethical clearance. Data collection, analysis and write up will take place over 42 months.

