It will be stated explicitly that participation may result in the parent's child attaining inadequate immunity to pneumococcal vaccine serotypes; however, the results of the trial will be reviewed by an Independent Data and Safety Monitoring Board and if there is evidence of inadequate immunity all children in the fractional dose arms will receive a 'top-up' full dose of PCV10.

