9.3.9 End of study visit

At 18 months of age, the parent and child will be invited back to the health facility for their final study visit. A single nasopharyngeal swab will be taken for analyses of carriage prevalence. Half of the participants in each of the trial arms A-F will have an additional small blood draw at this visit, as allocated during randomisation. The contact details of the parent will be updated and they will be informed that if results indicate that the fractional dose elicited an inferior immune response to the full dose, they will be asked to return to the study clinic one last time for a full dose to 'top-up' protection (if this is not known already).

To reduce loss to follow-up at the 18-month of age visit, the study team will contact participants by phone at around 13-17 months of age to remind them about their participation in the study and about the remaining final study visit.

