the 20% and the 40% doses may elicit inferior immunogenicity to the full dose in the fractional dose study arms [57]. The unprotected/partially protected children would then not benefit from direct protection of the vaccine but would benefit from the indirect protection generated by the continued routine administration of PCV10 in the national EPI programme, which has led to dramatic decreases in vaccine type carriage[85] and IPD[86]. In the Kilifi Health and Demographic Surveillance System (KHDSS) in 2016, there were 3.2 cases of vaccine-type IPD per 100,000 person years (pyo) in under 5s[87]. This amounts to 1 case every 31,250 person years. Among the 2100 trial participants followed for 1.5 years, we will observe a total of 3,150 pyo – which means there is a 10% chance that we will see one case of vaccine-type IPD in the study, and a 90% change we will see no vaccine-type IPD. one of the advantages of undertaking this study at KWTRP CGMR-Coast is that it has a strong history of IPD surveillance and we will therefore be able to detect IPD if it occurs in the trial population. Any cases observed will be reported to the DSMB. Although the risk of IPD is very small we will establish procedures to detect it at an early stage when treatment can avert a severe outcome; this will be done by providing participants with easy access to study medical staff. Children with signs of sepsis, pneumonia or meningitis will be investigated with bacterial culture of blood and/or cerebrospinal fluids as appropriate to detect the serotype of pneumococcus causing IPD. If any case of IPD occurs, it will be referred to the DSMB as an SAE. Members of staff at the hospitals in Kilifi and Malindi will be engaged by the study team to enable treatment of referrals if necessary and to notify the study team if a participant presents to the hospital in an unscheduled visit. Any child who develops vaccine type invasive pneumococcal disease will be unblinded and withdrawn from the study. If the child was allocated to a reduced dose arm, they will be given full dose PCV10 in three doses 4 weeks apart (if aged <12 months) or 1 dose (if aged ≥12 months).

If, after final analyses, the fractional doses are found to be inferior, all children in those groups will be given a single, full dose booster PCV.

The potential benefits of participation are as follows:

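### The trigger for the rescue full dose is worded as non-inferiority not met, as found inferior, and as inadequate immunity; these differ in criterion and timing, and nothing says which governs.

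*Combined protocol and SAP*

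**What the plan says.** Six places in the protocol describe when children in the fractional-dose arms would be offered an extra full dose.

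- Section 10.7, on results at 4 weeks after the third dose: "if the non-inferiority criteria are not met as per the statistical analysis plan, the DSMB will authorize unblinding".
- Section 10.5, at the same time point and in almost the same words: "if the non-inferiority criteria are not met as per the statistical analysis plan, the DSMB will authorise unblinding".
- Section 18.1: "If, after final analyses, the fractional doses are found to be inferior, all children in those groups will be given a single, full dose booster".
- Section 9.3.9, on what parents hear at the last visit: "if results indicate that the fractional dose elicited an inferior immune response to the full dose".
- Section 9.3.1, on what is stated at recruitment after mention of DSMB review: "if there is evidence of inadequate immunity all children in the fractional dose arms will receive a 'top-up' full dose of PCV10".
- Section 1, the lay summary, with the same timing as section 18.1: "the lower doses are found to not give a good enough immune response, all infants in those groups will be given a single booster".

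The only numerical post-boost criterion is in section 13.1: the lower confidence limit of the fractional/full GMC ratio must be at least 0.5, one month after the booster. Neither 'inferior' nor 'inadequate immunity' is defined. Section 13.3 leaves a detailed SAP to be finalised after the study has started.

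**The concern.** In a non-inferiority trial, failing to show non-inferiority and showing inferiority are different conclusions. An inconclusive result belongs to the first and not to the second. Inadequate immunity suggests a third kind of standard, an absolute level of antibody rather than a comparison between arms. The stated moment of decision also varies: a DSMB review of post-booster results in 10.5 and 10.7, final analyses in 18.1 and the lay summary.

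The rule drives the plan's trial-wide protective action. It can affect up to 4 × 300 = 1,200 infants and brings unblinding with it. If the wordings stay apart, the DSMB may face a result that meets one description and not another, and what parents were told may not match the criterion that is applied.

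**Working it through.** **The wordings side by side**

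| Section | Outcome | Timing |
|---|---|---|
| 10.5, 10.7 | Non-inferiority criteria not met | DSMB review of results at 4 weeks after dose 3 |
| 18.1 | Fractional doses found inferior | After final analyses |
| 9.3.9 | Inferior response to full dose | May be known only after the 18-month visit |
| 9.3.1 | Evidence of inadequate immunity | DSMB review of trial results |
| 1 | Response not good enough | After final analyses |

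The mismatch is visible without arithmetic. The rest shows whether plausible results would separate the wordings.

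**Inputs**
- Per arm: 300 enrolled with 5% loss (13.1), so 300 × 0.95 = 285.
- Margin 0.5 on the GMC ratio, 95% CI (13.1).
- Full-dose post-boost GMCs of 13 to 35 mcg/ml, which 13.1 takes from South African data on the PCV7 serotypes.
- SD of ln IgG: not stated. Section 13.1 hopes for a precision of ±2 to 4 mcg/ml. Pairing 13 with ±2 gives ln(1 + 2/13) × √285 / 1.96 = 1.23. Pairing 35 with ±4 gives ln(1 + 4/35) × √285 / 1.96 = 0.93. The pairing is my assumption. I use 1.24, with 0.93 as the lower case.

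**The plan's own figure**

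Section 13.1 states power above 99% for the GMC criterion. At a true ratio of 1, SE = 1.24 × √(2/285) = 0.1039, and power = Φ(0.693/0.1039 − 1.96) = Φ(4.71), or 99.9999% for one serotype. The figure reproduces, and holds for any ln-SD up to about 1.93.

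**One result under each wording**

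The CI multiplies and divides the observed ratio by exp(1.96 × SD × √(2/285)), which is 1.226 at SD 1.24 and 1.165 at SD 0.93.

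| Reading | Met when the observed ratio is below (SD 1.24) | SD 0.93 |
|---|---|---|
| Non-inferiority not met: lower limit < 0.5 | 0.613 | 0.582 |
| Inferior, as whole CI < 0.5 | 0.408 | 0.429 |
| Inferior, as whole CI < 1 | 0.816 | 0.858 |

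- Ratio 0.50, CI 0.408 to 0.613: non-inferiority is not met, but inferiority beyond the margin is not shown.
- Ratio 0.70, CI 0.571 to 0.858: non-inferiority is met, but the response is significantly lower than with the full dose.
- Ratio 0.45 with a full-dose GMC of 13: CI 0.367 to 0.552, so non-inferiority is not met. The fractional GMC is 0.45 × 13 = 5.85 mcg/ml, about 17 times 0.35. The share at or above 0.35 is Φ(ln(5.85/0.35)/1.24) = 98.8%, or 97.0% at SD 1.5.

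For SDs from 0.5 to 1.5 the order of the three cut-offs does not change. One case does not arise on these figures: failing non-inferiority while the CI still includes 1 needs an ln-SD above about 2.11.

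**The case against.** The strongest reply is that there is one operative rule. Sections 10.5 and 10.7 name the time point, the deciding body and the criterion, and they agree. The lay summary, 9.3.1 and 9.3.9 tell families about it in plain language, and 9.3.1 itself refers to DSMB review. The plan specifies no inferiority test, so 'inferior' may simply be shorthand for failing the non-inferiority test. On that reading the criterion in 18.1 and 9.3.9 matches 10.7 and only the timing in 18.1 differs. Much of this stands. It does not remove the point, because 18.1 is also protocol text making a direct commitment, and no sentence gives one wording precedence.

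Some stronger inferences are tempting and should not be drawn.

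- That one result both requires and forbids the dose, or that 18.1 and 9.3.9 promise no action on an inconclusive result. Each says what happens if a condition holds; none says only if.
- That the recipients differ. The children in the fractional arms, those groups, and fractional-dose recipients can all be the same 1,200 infants.
- That the products contradict each other. PCV10 in 9.3.1 is a specific case of the generic full dose in 10.5 and 10.7 and the generic booster in 18.1.
- That inadequate immunity must mean 0.35 mcg/ml per infant at 18 weeks. No section makes that link, and 13.2 also sets GMCs from the 9- and 18-month samples against the protection threshold.

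**Conclusion.** The point holds as a lack of equivalence between wordings, in both criterion and timing, with no stated order of precedence. It is not a demonstrated contradiction in what the DSMB must do: 10.5 and 10.7 are consistent and can be followed as they stand.

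On size, at 285 per arm and an ln-SD of 1.24, observed ratios between about 0.41 and 0.61 fail non-inferiority without showing inferiority beyond the margin (0.43 to 0.58 at SD 0.93). If 'inferior' means below 1, the mismatch runs the other way, for ratios between about 0.61 and 0.82. These bands are illustrative. They cover one serotype, while the endpoint covers 10 or 13, so they do not show when a whole arm would trigger. They also rest on an assumed SD and on readings of a word that the plan leaves undefined. The comparison with 0.35 borrows GMCs from another population and the PCV7 serotypes only.

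The length of any delay cannot be derived. Section 10.7 itself expects that some children may have left follow-up before the DSMB outcome is known, and section 17 puts completion of laboratory and data analysis together in months 34 to 42. The correction is worth making because it is cheap and the action may reach 1,200 infants.

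**What to change.** Reconcile the passages. State the trigger once, in section 10.7, fixing:

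- the outcome and the time point;
- whether a result that merely fails to show non-inferiority counts;
- whether the judgement is made arm by arm or for all fractional arms together;
- the product offered to the PCV13 arms.

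Then replace the sentences in sections 1, 9.3.1, 9.3.9, 10.5 and 18.1 with consistent text or a cross-reference to 10.7, and check that the SAP uses the same rule. The sponsor and DSMB choose the rule; this review takes no view on which it should be. Complete the change before the DSMB reviews results by arm.

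The cost is a wording amendment in six places, with no extra participants, samples or assays. The consent form is not among the pages available here, so whether it needs a matching line should be checked against the form itself.

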11 LAB PROCEDURES

11.1 Blood sample management & testing

Venous blood samples will be collected at baseline (2ml), the D84 visit (approximately 18 weeks of age; 2ml) and, in trial arms A-F, at the 1-month post-boost visit (10-13 months of age; 2ml). Half of the participants enrolled onto trial arms A-F (150 in each arm) will have additional blood draws at 9 months and 18 months of age (2ml at each visit). A cumulative total of 4-10mls of blood will be collected from each participant by the end of the trial, depending on randomisation and allocation. The sample at baseline will be tested for anaemia in order to inform clinical care of the infant. All serum will be separated within 48 hours of sample collection and stored at -20 degrees Celsius at the KWTRP CGMR-Coast laboratories. All samples will be shipped to the UCL WHO Reference Laboratory for Pneumococcal Serology based at the Great Ormond Street Institute of Child Health. If any remaining volume is not shipped to UCL, samples will be stored at the KWTRP CGMR-Coast laboratories. Sample management will include monitoring of the number of freeze-thaw cycles experienced by each sample in a laboratory database.

At the UCL WHO Reference Laboratory for Pneumococcal Serology, sera will be assayed for antibodies to all vaccine-type capsular polysaccharides using the WHO reference ELISA following adsorption with cell wall polysaccharide and 22F polysaccharide at a concentration of 10 mcg/ ml (Details available at <http://www.vaccine.uab.edu/ELISA%20Protocol.pdf>). This assay is based on the original Wyeth assay used to generate the correlate of protection of 0.35 mcg/ml.

A subset of 50 sera from each of the trial arms A-F, at the 1 month post-boost time point will be used to estimate the functionality of the immune response to all vaccine serotypes using the multiplexed Opsono-Phagocytic Assay (MOPA; details available at <http://www.vaccine.uab.edu/UAB-MOPA.pdf>).

The result of the mother's most recent HIV test will be recorded at the study screening visit using the information in their 'Mother & Child Health Handbook' or alternative clinical source notes, if unavailable, rapid diagnostic tests will be performed according to Government of Kenya guidelines. If a mother is living with HIV, a dry blood spot will be taken from the infant in order to process with PCR as per Government of Kenya guidelines. The result of the HIV test, performed at the national testing laboratory in Mombasa, will be recorded in the 'Mother & Child Health Handbook' or alternative clinical records and study clinical source documents, when the result becomes available.

